11 STATISTICAL CONSIDERATIONS

The study is characterized by an estimation- rather than hypothesis-driven approach. The aims of identification and quantification of dentists' selected treatment(s) for DH and methods selected for the diagnosis of DH in the practice setting will be addressed by estimation of percentages of dentists using each method and percentages of patients for which each method was used, and calculation of confidence intervals (CIs) to evaluate the precision of each estimate.

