Sample size requirements for the primary objective of characterizing the trajectories of patient-reported pain outcomes over the study period, and for comparing these changes among the different treatments selected by the practitioners, were based on the expected widths of 95% CIs for the percentages of use of each of the treatments and diagnostic methods, and secondarily on t tests for comparisons of changes in VAS scores between two treatments, adjusted for the effect of clustering and for multiple treatment comparisons, again in order to approximate the power of the proposed GEE analysis. Power was calculated for comparison of two groups because the actual number of treatments observed will not be known until after the data is collected. In the absence of information on group size, the sample was assumed to be equally divided. Power was calculated for the conventional "medium effect size", represented by a between-group difference in means equal to one-half of the within-group standard deviation. Additionally, the difference in means that would be detectable with 80% power was calculated, and expressed as a multiple of the within-group standard deviation. Expected CI widths were based on the Normal approximation to the binomial distribution, and were calculated around 50% in order to provide conservative estimation. Precision of estimation of mean change in pain scores was calculated based on the widths of 95% CIs for change in reported pain scores, also using the expected mean numbers of subjects in equal-sized treatment groups. These CIs are expressed in standard deviation units.

The actual analysis will compare all the treatment groups that occur in the study, using an analysis of variance approach which will incorporate the entire sample. While the groups will be smaller than in this approximation, this will be somewhat offset by incorporating the entire sample in calculation of the standard error, so that power will be greater than would be calculated using only a portion of the patients in separate pairwise comparisons of treatment groups.

The nQuery Advisor version 7.0 software package was used to calculate expected confidence interval widths and power estimates.

Outcome measure used for calculations

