The outcome measures that were used for sample size calculations for tabulation of treatment and diagnostic method use were the treatment techniques listed by the dentists and the diagnostic techniques, as presented in the dentist surveys. The sample size calculations for these are identical, but the number of treatment techniques is not known in advance, while we will know the number of diagnostic techniques that will be included. Patients' rating of DH using VAS responses were used as the outcome variable for evaluation of patient-reported pain outcomes over time.

Test statistic

Power for hypothesis testing was based on t tests and chi-square tests. Precision of estimation of percentages was based on widths of 95% confidence intervals for the binomial distribution. Precision of estimation of mean change in pain scores was based on widths of 95% confidence intervals for the normal distribution.

For the primary objective, study precision calculations were based on widths of 95% confidence intervals, rather than on power of hypothesis tests.

Type I error rate

The Type I error rate will be set at 5% for all analyses.

Type II error rate

The target Type II error rate is 20%, corresponding to statistical power equal to 80%. Power was calculated for a range of effect sizes, yielding ranges of power estimates.

Method for adjusting calculations for planned interim analyses, if any

No interim analyses are planned.

Assumptions used in calculations

[figure not shown]
Confidence interval width and power estimation for percentages of the dichotomous outcomes use of treatment modality and use of diagnostic techniques were based on

event rates of 50%, yielding the most conservative estimates by providing the widest estimated confidence interval width and a lower bound on power. This approach was used in order to somewhat offset possible inflation of power estimates due to approximation of equivalence of adjusted chi-square and t tests to the proposed GEE analysis, or to other errors of assumption in the calculations.

[figure not shown]
Data for objectives 1 and 2 are collected cross-sectionally, at a single patient visit. Thus, withdrawals are not anticipated for these analyses. For objective 3, loss to follow-up is a possibility. All available data for each patient will be used in the GEE analysis models. Least-squares adjusted means will be calculated in order to avoid biasing main effects means due to missing values.

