Present calculations from a suitable range of assumptions to gauge the robustness of the proposed sample size. Most assumptions are not accurate as point estimates.

[figure not shown]
Effective sample sizes were calculated for 180 dentists, 10 to 20 patients per dentist, and values of ICC from 0.00 to 0.05. Expected widths of 95% confidence intervals around a true proportion of 0.50 were calculated for each effective sample size. The value of 0.50 was used as this is the value that yields the maximum variance for a binomial distribution, for a given sample size. Thus, these calculations provide upper bounds for the widths of confidence intervals for each sample size, providing conservative estimates in case ICC is higher than expected. Effective total sample sizes for the different values of ICC and numbers of patients per dentist are presented in the following chart.

[figure not shown]
The expected widths of confidence intervals for the primary estimation aims are presented in the following chart. The first set of expected widths was calculated for the entire sample, to illustrate the total information content of the sample, given each of the sample size choices. These expected widths range from 3.3%, reflecting estimation within $\pm 1.65\%$, for 20 patients per dentist and ICC equal to 0.0, to 5.0%, reflecting estimation within $\pm 2.5\%$, for 10 patients per dentist and ICC equal to 0.05. As seen in the plot, increasing the number of patients per dentist from 10 to roughly 16 provides substantial increases in precision, with smaller gains in precision with increases to 18 or 20 patients per dentist.

Assuming that four main treatment groups occur, then the expected widths of 95% CIs on the percentages of patients in each of these subgroups would range from 13.1% (estimation within $\pm 6.5\%$) for 20 patients per dentist and ICC equal to 0.0 to 22.3% (estimation within $\pm 11.15\%$) for 10 patients per dentist and ICC equal to 0.05. The expected widths of these CIs are shown in the following chart, which presents the same pattern across sample sizes as that for the entire sample.

[figure not shown]

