11.2 Final Analysis Plan

Analysis plan for Primary Objectives:

#1. To characterize methods of diagnosing DH in the practice setting.

(This will done by asking questions by means of an online questionnaire on what practitioners usually do when diagnosing DH.)

Practitioners' responses to questionnaire items will be summarized and reported as frequencies and percentages. Ninety five percent confidence intervals will be calculated for percentages. The primary analytic approach for this Aim will not be based on hypothesis testing.

#2. To characterize dentists' selected treatment(s) of DH.

Analysis approach: This descriptive aim will be addressed by tabulating the treatment modalities used by practitioners during the study. Percentages of practitioners using each modality and percentages of total patients who received each modality will be calculated. Confidence intervals for percentages of patients receiving each of the treatment modalities will be calculated, with adjustment for clustering by dentist. Comparisons of percentages among the treatment modalities will be conducted using a mixed model logistic regression, to account for the effect of correlation due to obtaining multiple observations from each practitioner. A term representing the individual practitioner will be specified as a random effect in the analytic model, and estimation will be implemented using GEE. An indicator variable representing treatment modality will be included as a fixed effect.

#3. To characterize patient-reported pain outcomes over time.

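### The stated precision for the primary estimation aims (±1.65 to ±2.5 points) holds only for percentages of patients; percentages of practitioners have n = 180 and ±7.3 points, and the stated upper end does not follow from its own inputs

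*Protocol*

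**What the plan says.** Section 11 of the protocol calls the study estimation-driven and names two kinds of percentage for diagnosis and treatment: "estimation of percentages of dentists using each method and percentages of patients for which each method was used", each with a confidence interval.

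Section 11.1 sizes the study on interval widths for patients clustered within practices. "Effective sample sizes were calculated for 180 dentists, 10 to 20 patients per dentist, and values of ICC from 0.00 to 0.05". For every one of these, the plan then works out how wide an interval would be if half of the patients had the characteristic. The result is introduced with "The expected widths of confidence intervals for the primary estimation aims are presented in the following chart": 3.3% (±1.65) for 20 patients per dentist at ICC 0, up to 5.0% (±2.5) for 10 per dentist at ICC 0.05. The outcomes behind the calculation are described as "the treatment techniques listed by the dentists and the diagnostic techniques, as presented in the dentist surveys". Using 0.50 is said to give upper bounds on the widths, "providing conservative estimates in case ICC is higher than expected". The chosen design is 180 dentists with 14 patients each.

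Section 11.2 analyses Objective 1 from an online questionnaire about usual diagnostic practice: practitioners' "responses to questionnaire items will be summarized and reported as frequencies and percentages", with 95% intervals. Objective 2 tabulates the treatments used during the study and reports both percentages of practitioners and percentages of patients.

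**The concern.** The widths are labelled as those of the primary estimation aims and tied to survey answers, yet they are computed from between 1,241 and 3,600 effective patients. A questionnaire completed once per practitioner yields at most 180 answers. In an estimation-driven study these widths are the design justification, so a reader would expect a diagnostic-method percentage to be known to within about 2 points when the design gives about 7.

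The design reasoning is affected as well. Section 11.1 presents the move from 10 to about 16 patients per dentist as a substantial gain in precision. For percentages of practitioners it gains nothing. Section 11.1 also treats the loss of 10 practitioners only as a fall to 2,380 patients, whereas for Objective 1 it means n = 170.

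For percentages of patients, the text offers the choice of 0.50 as a safeguard against a high ICC, which is a different source of error.

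**Working it through.** **Inputs (Sections 11.1 and 11.2).** 95% two-sided intervals. "Expected CI widths were based on the Normal approximation to the binomial distribution, and were calculated around 50% in order to provide conservative estimation". There are 180 dentists, 10 to 20 patients each (14 chosen), ICC 0 to 0.05, and up to 10 practitioners lost.

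**Formulas.** With k dentists, m patients per dentist and ICC ρ: n_eff = k·m / (1 + (m − 1)ρ), and width = 2 × 1.96 × √(p(1 − p)/n_eff).

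**1. The plan's own figures.**
- m = 20, ρ = 0: n_eff = 3,600, width 3.27% (±1.63). This agrees with the stated 3.3%.
- m = 10, ρ = 0.05: n_eff = 1,800/1.45 = 1,241, width 5.56% (±2.78). The stated 5.0% (±2.5) is not reproduced.
- Variants tried for the second case: continuity correction 5.64%, design effect 1 + mρ 5.66%, 90% interval 4.67%. None gives 5.0%. A width of 5.02% does arise at m = 14 with ρ = 0.05, and at m = 10 with ρ = 0.02.
- Cross-check: the plan's four-group widths for the same two configurations are 13.1% and 22.3%, a ratio of 1.70. The recomputed whole-sample widths give 5.56/3.27 = 1.70; the stated ones give 5.0/3.3 = 1.52. Only the ratio is used here. The absolute four-group widths are a separate matter, since a quarter of each sample would give 6.53% and 11.13%.

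**2. Percentages of practitioners.** One observation per practitioner, n = 180:
- At 50%: 1.96 × √(0.25/180) = ±7.30 points, width 14.6%. For 90 of 180, the exact interval is 42.5% to 57.5% (±7.5) and the Wilson half-width is 7.2.
- At 30%, 20% and 10%: ±6.7, ±5.8 and ±4.4.
- With 170 practitioners, at 50%: ±7.5.
- Against the stated half-widths: 7.30/2.5 = 2.9 and 7.30/1.65 = 4.4.

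**3. Percentages of patients, 14 per dentist, p = 0.50.**

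| ICC | n_eff | Width | Status |
|---|---|---|---|
| 0 | 2,520 | 3.9% | in the plan's range |
| 0.05 | 1,527 | 5.0% | in the plan's range |
| 0.1 | 1,096 | 5.9% | assumed |
| 0.2 | 700 | 7.4% | assumed |
| 0.5 | 336 | 10.7% | assumed |

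**4. What 0.50 protects against.** At 14 per dentist and ICC 0.05 the design effect is 1 + 13 × 0.05 = 1.65. If the true percentage is 20%, the variance ratio is 0.25/0.16 = 1.56, so the 5.0% width still holds up to a design effect of 1.65 × 1.5625 = 2.58, which is ICC (2.58 − 1)/13 ≈ 0.12. At a true 10%, the same steps give 4.58 and ICC ≈ 0.28. At a true 50% there is no slack.

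**The case against.** Percentages of patients are also a primary estimand. For Objective 2, Section 11.2 specifies clustering-adjusted intervals for exactly those, and for them the patient is the right unit. This stands: a reader might infer that ±7.3 replaces every primary width, and the documents do not support that. A practitioner-level figure is missing from the text; the patient-level ones are not misplaced for their own estimand.

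Section 11.1 also says that the whole-sample widths illustrate the information content of the sample. That softens the label, but the sentence just before it assigns the widths to the primary estimation aims.

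Choosing 0.50 does give slack when a method's true percentage is far from 50%, as step 4 shows, and Section 11.1 elsewhere says that it was meant to offset errors of assumption to some extent. So to say that it gives no protection at all would go too far. What fails is the claim of an upper bound.

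A reader might also infer that the ICC for treatment choice must exceed 0.05, because Section 3.2.1 speaks of preferred methods. That wording describes the questionnaire, and the documents give no ICC estimate. Values above 0.05 are assumptions here.

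Lastly, the planned intervals for Objective 1 would be computed from practitioners' responses, so no reported result is biased, and ±7.3 may well be adequate for a descriptive survey. That limits the seriousness but does not make the stated figure right.

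**Conclusion.** The concern holds in this form. The widths of 3.3% to 5.0% describe percentages of patients only. Objective 1 (one questionnaire per practitioner) and Objective 2's percentages of practitioners (from treatments used during the study, not from questionnaires) have n = 180, hence ±7.3 points at 50%, or ±7.5 with 170 practitioners. The readable text states no such figure; the charts could not be seen, but the text describes them as varying patients per dentist and ICC.

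For percentages of patients, the widths are not upper bounds once the ICC exceeds 0.05, although there is slack away from 50%. The stated upper end should be 5.6%, not 5.0%.

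These results rest on the plan's own convention (Normal approximation, 50%), on independent practitioners, and on full response from all 180. This is a misstatement of precision. It is not evidence that the sample is too small.

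One inconsistency remains open. Section 11 promises percentages of patients for each diagnostic method, Section 3.2.1 mentions visit forms, and Section 11.1 says that the data for Objectives 1 and 2 come from a single patient visit. Section 11.2 analyses Objective 1 from the questionnaire alone.

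**What to change.** - Add practitioner-level precision to Section 11.1: ±7.3 points at 50% with n = 180, for Objective 1 and for all percentages of practitioners. State that patients per dentist does not affect it.
- Keep the patient-level widths, label them as applying to percentages of patients, and correct 5.0% to 5.6% for 10 per dentist at ICC 0.05. Give the chosen design of 14 per dentist explicitly: 3.9% at ICC 0 to 5.0% at ICC 0.05. Add a sensitivity range marked as assumed: 5.9% at 0.1, 7.4% at 0.2 and 10.7% at 0.5.
- Delete the statement that the widths are conservative if the ICC is higher than expected, or limit it to true percentages far from 50%.
- Reconcile Sections 3.2.1, 11, 11.1 and 11.2 on whether Objective 1 also reports percentages of patients per diagnostic method from visit forms. If it does, use intervals clustered by practitioner.

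The cost is restated figures and, depending on the last item, one more tabulation. No patients or dentists are added. The stated precision becomes less favourable.

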Precision of estimation of mean change in reported pain scores is shown in the following chart. Four equal-sized subgroups of the total sample were assumed. Widths were calculated for CIs within a single subgroup. Precision is represented as the widths of 95% confidence intervals, based on the Normal distribution, in units of standard deviation of the change scores.

[figure not shown]

Power to detect a medium effect size for difference in VAS score between treatments is approximately 100% for all effective sample sizes that were considered. Differences between group means that would be detectable range from 0.095sd for 20 patients per dentist and ICC equal to 0.0 to 0.160sd for 10 patients per dentist and ICC equal to 0.05. Thus, all configurations that were considered provide substantial power to detect very small effect sizes, yielding confidence that the study will be adequately powered,

even if ICC is larger than those assumed in the power calculations. Power to detect a difference between treatment group means is shown in the following chart.

Given the results of these power calculations and practical considerations, we will recruit 180 dentists, who will each recruit 14 patients, for a total sample size of 2,520 patients. This will provide protection against loss of power due to potential dropout of patients or of dentists, and against finding larger than expected correlation among observations made by the same dentists. If a patient loss to follow-up of 20% were to occur, the study would still include 2,016 patients, which would still provide essentially 100% power to detect a medium effect size, for likely magnitudes of ICC. Similarly, while it is unlikely that practitioner dropout will occur, loss of as many as 10 practitioners would result in a total expected sample size of 2,380 patients, again providing very high power if ICC is of the expected magnitude. The proposed sample size provides substantial protection against the possibilities that ICC might be higher than anticipated or that the effect size might be smaller than anticipated.

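### The VAS detectable differences of 0.095 to 0.160 SD are described as adjusted for multiple treatment comparisons but are unadjusted two-group figures; with the four groups assumed elsewhere in the section they are about 0.16 to 0.27 SD

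*Protocol*

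**What the plan says.** All of this is in Protocol Section 11.1.

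- The secondary basis for sample size on the pain objective is "t tests for comparisons of changes in VAS scores between two treatments, adjusted for the effect of clustering and for multiple treatment comparisons".
- The number of groups is two: "Power was calculated for comparison of two groups because the actual number of treatments observed will not be known". On their size: "In the absence of information on group size, the sample was assumed to be equally divided".
- On error rates: "The Type I error rate will be set at 5% for all analyses". The power target is 80%.
- The results are given as: "Differences between group means that would be detectable range from 0.095sd for 20 patients per dentist and ICC equal to 0.0 to 0.160sd", the second figure being for 10 patients per dentist and ICC 0.05. For the half-SD effect: "Power to detect a medium effect size for difference in VAS score between treatments is approximately 100% for all effective sample sizes".
- From these results the section concludes that every configuration has ample power for very small effects.
- The section also says that the real analysis will compare all treatment groups that occur, that these will be smaller than the two halves, and that using the whole sample for the standard error partly makes up for this. Its precision calculations, for percentages and for mean change in pain, assume four treatment groups.

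**The concern.** A stated multiplicity adjustment should appear in the numbers. If the detectable differences equal the plain 5% two-group values, the text credits them with a property that they lack.

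The same figures then support a conclusion about a comparison of several groups. Two halves of the sample give the smallest detectable difference of any split, so moving to more and smaller groups, with adjustment, can only raise it. A reader of the protocol would expect differences of 0.10 to 0.16 SD between treatments to be found with 80% power, which does not hold once there are four groups.

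**Working it through.** **Inputs, all from Section 11.1 unless marked.** 180 dentists; m = 10 to 20 patients per dentist, 14 chosen; ICC 0.00 to 0.05; 5% type I error; 80% power; SD = 1 because effects are in SD units. Assumption: the test is two-sided, since the protocol does not say.

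**Formulas.** Effective N = 180m / (1 + (m − 1) × ICC). Detectable difference = (critical value + 0.8416) × √(2/n), with n the effective number per group.

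**Step 1: reproduce the stated figures** (two halves, critical value 1.960).

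- m = 20, ICC 0: effective N = 3,600 and n = 1,800. The difference is 2.8016 × √(2/1,800) = 0.0934 SD (stated 0.095).
- m = 10, ICC 0.05: effective N = 1,800/1.45 = 1,241.4 and n = 620.7. The difference is 2.8016 × √(2/620.7) = 0.1590 SD (stated 0.160).

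Unadjusted power at the stated differences is 81.3% and 80.5%. The two-sided alpha that they imply is 0.045 and 0.048. The clustering adjustment is therefore in the figures, and the small gaps are of rounding size.

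**Step 2: see whether any multiplicity adjustment fits** (still two halves).

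| Test | m = 20, ICC 0 | m = 10, ICC 0.05 |
|---|---|---|
| Stated in protocol | 0.095 | 0.160 |
| Unadjusted, two-sided 5% | 0.093 | 0.159 |
| Bonferroni, 2 comparisons | 0.103 | 0.175 |
| Bonferroni, 3 comparisons | 0.108 | 0.184 |
| Bonferroni, 6 comparisons | 0.116 | 0.198 |
| Unadjusted, one-sided 5% | 0.083 | 0.141 |

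Only the unadjusted two-sided row fits at both ends.

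**Step 3: four equal groups, n = effective N / 4.** Tukey critical value over the six pairs: studentized range quantile/√2 ≈ 2.57.

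| Configuration | Effective N | n per group | Unadjusted | Tukey |
|---|---|---|---|---|
| m = 20, ICC 0 | 3,600 | 900 | 0.132 | 0.161 |
| m = 10, ICC 0.05 | 1,241.4 | 310.3 | 0.225 | 0.274 |
| m = 14, ICC 0 | 2,520 | 630 | 0.158 | 0.192 |
| m = 14, ICC 0.05 | 1,527.3 | 381.8 | 0.203 | 0.247 |
| m = 14, 20% loss, ICC 0.05 | 1,335.1 | 333.8 | 0.217 | 0.264 |

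The 20%-loss row uses 2,016 patients, or 11.2 per dentist: 2,016/1.51 = 1,335.1. In the first two configurations, Tukey-adjusted power at the protocol's own 0.095 and 0.160 SD is about 29% and 28%.

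**Step 4: the pooling remark.** Estimating the SD from all groups adds degrees of freedom but leaves the 2/n term unchanged. The calculation above already treats the SD as known, so it includes the whole benefit of pooling.

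**Step 5: power for 0.5 SD.** With four Tukey-adjusted groups it is above 99.9% in every row above. As an illustration only, take eleven equal, exclusive groups, the number of modality categories in Section 3.2.1 (critical value 3.22), at m = 14 and ICC 0.05. Then n = 138.8, the detectable difference is 0.488 SD, and power for 0.5 SD is about 83%. After 20% loss these become 0.522 SD and 75%.

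**The case against.** **The split is disclosed.** The protocol says that it used two equal halves, gives the reason, and warns that real groups will be smaller. That stands: the split is no concealed error. It does not excuse the adjustment that is claimed but absent, nor a conclusion that drops the warning.

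**The study is mainly about estimation.** Section 11 says so, precision for the primary objective rests on confidence interval widths, and the t tests are secondary. This stands and lowers the weight of the point. It does not remove it: the section cites the power results when fixing 2,520 patients, and Section 11.2 makes the time-by-treatment interaction the test of primary interest for pain.

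**Tukey is not prescribed for pain.** True; Section 11.2 names it only for satisfaction, so it serves here as one reasonable form of the unnamed adjustment. Bonferroni over six pairs gives nearly the same values (0.196 to 0.252 SD at 14 per dentist). Group size alone, unadjusted, already gives 0.158 to 0.203 SD.

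**The full design effect may be pessimistic.** It is the protocol's own method. If treatments were spread evenly within dentists, the contrast variance would be near 2(1 − ICC)/n. At 14 per dentist and ICC 0.05 the four-group Tukey value would then be about 0.19 SD rather than 0.25. The truth probably lies between.

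**A stronger reading that fails.** A reader might infer that the plan itself compares eleven groups and so can detect only about 0.4 to 0.5 SD. Section 3.2.1 lists categories to be recorded, among them no treatment, advice and a residual class, and allows several treatments at once. They are neither exclusive nor declared as comparison groups. Nor do the documents state any equivalence claim that a null result would feed.

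The chart of power for differences in treatment means was not visible in the text reviewed, so whether it shows adjusted curves could not be checked.

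**Conclusion.** The point holds as an error in stated figures. The detectable differences in Section 11.1 lack the multiplicity adjustment claimed for them. With the four groups that the section assumes for precision, they rise by a factor of about 1.7 when both group size and adjustment are accounted for (0.161/0.093 and 0.274/0.159). This rests on a two-sided test, equal groups and the protocol's design effect; unequal groups would make the smallest contrasts worse.

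The conclusion about very small effects is not supported for a four-group comparison, and the offset from pooling is negligible. The near-100% power for 0.5 SD is right for two or four equal groups but not for any number of groups. Nothing here shows that the sample size is too small. This is a worthwhile correction and not one on which the study depends.

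**What to change.** In Section 11.1:

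1. Preferably, restate the detectable differences for four equal groups with the adjustment named. With Tukey these are 0.16 SD (20 per dentist, ICC 0) to 0.27 SD (10 per dentist, ICC 0.05), 0.19 to 0.25 SD at 14 per dentist, and 0.26 SD with 20% loss and ICC 0.05. At the least, delete the mention of multiple treatment comparisons and label 0.095 to 0.160 SD as unadjusted two-group values.
2. Remove the conclusion about very small effects and the statement that pooling the standard error offsets smaller groups.
3. Limit the near-100% power for 0.5 SD to two or four equal groups. If a case with more groups is shown, mark it as an assumption.
4. State that the test is two-sided, and check that the power chart matches the restated figures.

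The cost is a few sentences and less flattering numbers. No patients, visits or analyses are added.
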